3.3. Study Treatment and Rationale

The study treatment is gildeuretinol acetate (ALK-001, C20-D3-retinyl acetate), a chemically modified vitamin A designed as a replacement for natural vitamin A. ALK-001 has been modified specifically to slow down the formation of toxic vitamin A dimers in the eye while not impairing the visual cycle. Because of its chemical structure, ALK-001 is expected to behave identically to natural vitamin A and to have the same pharmacokinetics and ADME profiles as natural vitamin A. As such, similarly to supplementation with natural vitamin A, ALK-001 will be administered orally at 14 mg/day.

Vitamin A dimers have been implicated in the pathogenesis of AMD because of their toxicity to retinal cells, and as they form and accumulate in the retina with age. The study overall hypothesis is to assess the extent to which slowing vitamin A dimerization by replacing vitamin A with gildeuretinol slows the progression of the growth of GA lesions.

4.0. STATISTICAL ANALYSIS CONVENTIONS AND DEFINITIONS

4.1. Reporting Conventions

Individual subject data obtained from electronic case report forms (eCRFs), external sources, and any derived data will be presented in data listings by subject.

Continuous measures will be summarized by number of observations, minimum, first quartile (Q1), median, mean, third quartile (Q3), maximum, and standard deviation (SD). The minimum and maximum will be presented at the same level of precision (decimal point) of the measurements. Median, Q1 and Q3, and mean will be presented at one greater level of precision (decimal point) as the measurements. SD will be presented at two greater levels of precision. In general, the number of decimal places should not exceed 3 decimal places unless appropriate. Confidence intervals (CIs) will be provided with the same decimal places as the point estimate, unless otherwise specified, in the tables and listings.

Categorical (including binary) measures will be summarized by count and percent. Categories for which counts are 0 will be displayed for the sake of completeness. For example, if none of the subjects discontinue due to “lost to follow-up”, this reason will be included in the table with a count of 0. A row denoted as “Missing” will be included in the count tabulations where necessary to account for dropouts or missing values. Percentages will be rounded to one decimal place, unless otherwise specified.

In general, all eyes of all subjects will be included in analyses, unless otherwise noted. The primary efficacy analysis will be conducted at a significance level of 0.05. Hypothesis testing for the key secondary objectives will be conducted with significance determined at the 0.05 level with multiple testing adjustments (Refer to [Section 6.2.1](#)). For most analyses, when a hypothesis test is performed, it will be comparing the ALK-001 and Placebo treatment arms. Confidence intervals will generally be given at a level to mimic the significance level (95% CIs for 0.05 significance level) unless otherwise noted.

Unless otherwise specified, the following treatment arms will generally be included in tables, listings, and figures:

- ALK-001: Subjects randomized to 24 months of ALK-001 at 14 mg per day
- Placebo: Subjects randomized to 24 months of placebo

All analyses will be conducted in SAS®, Version 9.4 or higher (SAS Institute Inc., Cary, NC) or in R, Version 3.6.0 or higher (R Core Team 2019).

4.2. Reference Start Date and Study Day

Reference start date is defined as the date of the first study drug administration following the end of the run-in period, which is designated as Day 1, and the preceding day is Day -1, etc.

Study day will be calculated from the reference start date and will be used to show the start/end day of assessments or events.

Study day will be computed as follows:

- Study Day = Assessment/event date – reference start date + 1 if the assessment/event date is on or after the reference start date.
- Study Day = Assessment/event date – reference start date if the assessment/event date is before the reference start date.

In the situation where the assessment/event date is partial or missing, study day and any corresponding duration will appear as partial or missing in the listings.

4.3. Definition of Baseline

The baseline for efficacy and safety parameters will be defined as the last non-missing assessment obtained prior to the first study drug administration.

4.4. Analysis Visit Window

Unless otherwise specified, the actual scheduled nominal post-baseline visit will be used for by-visit summaries. Post-baseline unscheduled visits and early termination visits will be mapped to a scheduled visit and will only be used in the analysis if the nominal scheduled visit result is missing. [Table 1](#) and [Table 2](#) presents the analysis visit window mapping for unscheduled and early term visits. In the case that multiple unscheduled or early termination visits are in the same analysis window, the one closest to the target date will be used. If multiple assessments are of the same distance from the target day for a particular analysis window, the later assessments will be used.

Table 1: 6-Month Interval Analysis Visit Window for Unscheduled and Early Termination Visits

Analysis Visit	Target Start Day ^a	Analysis Window Study Day ^a	
		Lower	Upper
Month 6	180	91	270
Month 12	360	271	450

Analysis Visit	Target Start Day ^a	Analysis Window Study Day ^a	
		Lower	Upper
Month 18	540	451	630
Month 24	720	631	End of study

^a Study day will be calculated from the reference start date.

Table 2: 12-Month Interval Analysis Visit Window for Unscheduled and Early Termination Visits

Analysis Visit	Target Start Day ^a	Analysis Window Study Day ^a	
		Lower	Upper
Month 12	360	181	540
Month 24	720	541	End of study

^a Study day will be calculated from the reference start date.

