#### **1.14.3 Follow-up After Early Treatment Interruption; Early Termination Visit**

Subjects who temporarily interrupt treatment do not have any special follow-up and may simply continue according to the planned schedule.

Subjects who permanently interrupt treatment will be requested to return the study drug to the site (which may be done by mail), and may be invited to return to the site for an Early Termination visit (ET) (see section 1.2) if a minimum of approximately 1 month has elapsed following the last in-person visit. The ET visit should take place as soon as possible, preferably within 1 month of the permanent treatment interruption. During the ET visit, the following assessments shall be performed in addition to all routine care assessments:

- Physical and ocular examination
- AE
- Concomitant Medications
- Vital signs
- Collection of study drug
- Clinical lab (biochemistry, hematology, lipid, pharmacokinetics, and other optional testing as requested by sponsor)
- ECG: perform if previous ECG is older than ~4 months
- BCVA, LLVA, reading speed: perform if previous testing is older than ~4 months
- Fundus autofluorescence and OCT: perform if previous testing is older than ~4 months

- Microperimetry: perform if previous microperimetry is older than ~4 months
- Fluorescein Angiogram: perform if previous FA is older than ~one year
- Vision questionnaires: perform if previous questionnaires are older than ~6 months

Study team may consult with sponsor to determine if certain activities are required. At the completion of the ET visit, subjects' participation should be discontinued and all study drug returned to the site. There should be no additional follow-up visits.

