#### 1.14.4 Temporary or Permanent Interruption of Treatment

Abrupt interruption of treatment is not expected to adversely affect subject health and therefore no special precaution is needed when interrupting treatment. Sponsor shall be informed of any treatment interruption.

- If investigator and sponsor both agree that it is not in the best interest of the subject to continue treatment, for reasons including but not limited to, **non-compliance or health risk**, the subject shall interrupt treatment. Interruption may be temporary if the health risk is expected to resolve in a reasonable time. Subject may be allowed to resume treatment upon mutual decision by investigator and sponsor. In this case, off-treatment duration shall be documented.
- If subject's **treatment assignment is unmasked**, subject shall interrupt treatment, unless decided otherwise by sponsor.
- If a subject's level of **either AST, ALT or Alk Phos is greater than 5 times the upper limit normal (>5x ULN)** for laboratory reference range, subject should interrupt treatment immediately and permanently.
- If a subject's level of **either AST, ALT or Alk Phos is greater than 3 times the upper limit normal (>3x ULN)** for laboratory reference range, subject should be re-tested within 2 weeks. Temporary interruption of treatment is not required until re-test. If subject is unable to be re-tested within 2 weeks, subject should temporarily interrupt treatment until re-test can be performed. If at re-test, the obtained values are lower than 3 times the ULN, the subject can continue or resume treatment. If at re-test the obtained values are still higher than 3 times the ULN, the subject shall interrupt treatment, at least until these levels are measured to be below 3 times the ULN. Once this is the case, subject shall be allowed to resume treatment only upon approval by sponsor.
- Subject shall immediately interrupt treatment if subject is **presumed to have liver injury** according to Hy's law, as indicated by either of the following (assuming no other reason can be found to explain the combination of increase in aminotransferase and bilirubin, including for example alcohol ingestion, congestive heart failure, hepatitis, other drugs, preexisting liver disease, etc.)

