7.3. Laboratory Tests

Laboratory tests, including laboratory parameters in chemistry, hematology, and lipids panel, are required at V01 (Screening), V04 (Month 6), V06 (Month 12), V08 (Month 18), V10 (Month 24), optional at all other visits.

Descriptive statistics for values and changes from baseline for laboratory results will be summarized by treatment arm and visit for chemistry, hematology, and lipids panel parameters listed in [Appendix 2](#).

The numbers and percentages of subjects for each laboratory parameter with quantitative laboratory values categorized as low, normal, and high, will be summarized by treatment arm and visit. Shift table in laboratory results (low/normal/high) from baseline to each post-baseline visit for each laboratory parameter will also be presented.

In accordance with the FDA guideline on Drug-Induced Liver Injury (*Drug-Induced Liver Injury: Premarketing Clinical Evaluation (2009) Section E2*)), following occurrences will be summarized by treatment arm and visit:

- Elevations greater than 3, 5, 10, and 20 times the upper limit of normal for AST, ALT, and either AST or ALT
- Elevations of bilirubin greater than 2 times the upper limit of normal
- Elevations of alkaline phosphatase greater than 1.5 times the upper limit of normal
- Elevations of ALT or AST greater than 3 times the upper limit of normal accompanied by elevations of bilirubin greater than 1.5 or 2 times the upper limit of normal.

The mean change from baseline \pm the standard error for laboratory parameters: ALT, AST, total bilirubin, triglycerides, HDL and LDL, will be plotted over time by treatment group.

All laboratory data will be listed.

There will be no imputation for missing laboratory results. For quantitative laboratory results reported as ' $<X$ ' or ' $\leq X$ ' or ' $>X$ ' or ' $\geq X$ ', a value of X will be used in the summary tables. The actual results as collected will be displayed in the listings.

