7.4. Vital Signs

Vital signs collected include BMI (calculated from weight and height), body temperature, respiratory rate, heart rate, and blood pressure (systolic and diastolic), are required at V01 (Screening), V02 (Randomization / Day 1), V04 (Month 6), V06 (Month 12), V08 (Month 18) and V10 (Month 24), optional at V03 (Month 3), V05 (Month 9) and V07 (Month 15), V09 (Month 21).

Descriptive statistics for values and changes from baseline for each vital sign parameter will be summarized treatment arm and visit.

All vital sign results will be listed.

7.5. 12-Lead ECG

ECG measurements, including QT interval corrected by the Fridericia's formula (QTcF) and interpretation of ECG results (normal, abnormal not clinically significant, abnormal clinically significant), are required at V01 (screening), V06 (Month 12) and V10 (Month 24), optional at V05 (Month 9) and V07 (Month 15).

Descriptive statistics for values and changes from baseline for QTcF will be summarized by treatment arm and visit.

The numbers and percentages of subjects will be summarized by treatment arm and visit for QTcF >450 , >480 and > 500 msec and for QTcF change from baseline >30 and > 60 msec, respectively.

The numbers and percentages of subjects whose ECG interpretations by the investigator were normal, abnormal not clinically significant, and abnormal clinically significant will be summarized by treatment arm and visit.

All ECG results will be listed.

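### Liver and QTcF threshold counts are by visit only, with no worst post-baseline summary, so liver retests and early termination results can be left out

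*SAP*

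**What the plan says.** SAP 4.4 bases by-visit summaries on the nominal scheduled visit unless a section specifies otherwise. Unscheduled and early termination results are mapped to a scheduled visit but "will only be used in the analysis if the nominal scheduled visit result is missing". If several fall in one window, "the one closest to the target date will be used".

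SAP 7.3 introduces its drug-induced liver injury counts with "following occurrences will be summarized by treatment arm and visit". These cover AST/ALT multiples of ULN, bilirubin, alkaline phosphatase, and ALT or AST above 3 × ULN accompanied by raised bilirubin. SAP 7.5 does the same for ECG: "The numbers and percentages of subjects will be summarized by treatment arm and visit for QTcF", followed by the absolute and change thresholds. Neither section makes an exception to 4.4, and neither adds a worst-value or any-time row.

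Protocol v1.1, Section 1.14.4, says that after AST, ALT or alkaline phosphatase above 3 × ULN the "subject should be re-tested within 2 weeks". Section 1.14.3 invites subjects who stop treatment permanently to an early termination visit "if a minimum of approximately 1 month has elapsed following the last in-person visit". That visit includes clinical labs and, conditionally, an ECG ("ECG: perform if previous ECG is older than ~4 months").

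**The concern.** Liver enzyme elevation is a named risk in protocol 1.5.8.1, and SAP 7.3 sets up its table specifically to look for drug-induced liver injury. Such a table should show how high each subject went and whether transaminases and bilirubin rose together. A rule that prefers the scheduled draw, and otherwise the draw nearest the target day, does not select on height.

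A subject whose ALT first passes 5, 10 or 20 × ULN at a retest or early termination draw can be shown in a lower category. So can one whose bilirubin first rises there. Even without unscheduled data, by-visit rows do not give the number of distinct subjects who ever crossed a threshold. The same applies, less strongly, to QTcF.

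**Working it through.** The point concerns a data-selection rule, so there is no plan figure to reproduce. The check maps protocol-generated results onto the SAP windows.

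**Inputs**

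- SAP 4.4, Table 1: Month 6 = Days 91–270, Month 12 = 271–450, Month 18 = 451–630, Month 24 = 631 to end. Targets are Days 180, 360, 540 and 720.
- SAP 4.4, Table 2: Month 12 = Days 181–540, Month 24 = 541 to end.
- Protocol 1.2, footnote 11: visits on the target day or up to one week early.
- Protocol 1.14.4: retest 1–14 days after the triggering draw.
- SAP 7.3: labs are required at Months 6, 12, 18 and 24.

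**1. Retests after a required lab visit**

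| Visit | Visit days | Possible retest days | Table 1 window |
|---|---|---|---|
| Month 6 | 173–180 | 174–194 | 91–270 |
| Month 12 | 353–360 | 354–374 | 271–450 |
| Month 18 | 533–540 | 534–554 | 451–630 |
| Month 24 | 713–720 | 714–734 | 631–end |

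There are 4 visits × 8 visit days × 14 retest days = 448 combinations, and all 448 fall in the triggering visit's own window. That visit already has a result, so the retest is not used. Late visits do not rescue it: for Month 6 the last visit day that keeps a 14-day retest inside the window is 270 − 14 = 256, which is 76 days late.

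**2. Retests after an optional visit** (taken as Days 90, 270, 450, 630 or up to 7 days early; the SAP gives no target for these)

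Of 448 combinations, those on or before the window boundary number 0 + 1 + … + 7 = 28 per visit.

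- After V03, these 28 have no window.
- After V05, V07 and V09, 3 × 28 = 84 map back to the previous required visit.
- The remaining 448 − 112 = 336 map to the next required visit and count only if that result is missing.

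**3. Early termination labs** at least 30 days after an attended Month 6, 12 or 18 visit and still in its window: Days 210–270, 390–450 and 570–630. Each range is 61 days (for example 270 − 210 + 1).

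**4. Days with no window at all:** 90 of 720 (12.5%) under Table 1; 180 of 720 (25%) under Table 2.

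**5. ECG**

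- Duplicate tracings at a scheduled visit belong to that visit and are unaffected. Only clinically indicated or early termination ECGs are at risk.
- With about 4 months taken as 120 days, an early termination ECG after a Month 12 ECG can occur from Day 360 + 120 = 480.
- Under Table 2, Days 480–540 (61 days) map to Month 12, so the ECG is left out. Under Table 1 the same days map to Month 18, where no ECG is scheduled, so it would be used. The SAP does not say which table governs ECGs.
- Protocol 1.2, footnote 18, allows the mid-study ECG at V05, V06 or V07, so by-visit rows can split one planned assessment over three visits with no any-time total.

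**The case against.** The best counter-argument is that other outputs already show these cases.

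- Protocol 1.16.1.6 makes a laboratory abnormality an adverse event if it needs treatment interruption, closer follow-up or further investigation. A value that triggers a retest arguably qualifies. The recorded severity must be updated if the event worsens.
- Protocol 1.14.4 requires interruption for a presumed Hy's law case, which should place it among the interruption TEAEs in SAP 7.2. Those tables are per subject and not restricted by visit windows.
- All laboratory and ECG results are listed.
- Few cases are expected. Protocol 1.16.1.6 quotes a 0.67% chance per subject of a random elevation to 2 × ULN. In 200 randomized subjects that is 200 × 0.0067 ≈ 1.3, and fewer would pass 3 × ULN.
- The 448 count only reflects wide windows. A quarter of it (112) follows Month 24, when treatment has ended and the retest rule may no longer apply.
- Table 1 naturally suits 6-monthly labs, so the 25% figure does not bear on them. The early termination ECG range assumes the mid-study ECG was done at Month 12.

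Most of this stands as a limit on weight, and none of it removes the gap. Adverse event tables count preferred terms and depend partly on investigator judgement; they do not give ULN multiples by arm. Listings give no comparative count. The 0.67% is a background rate for a different threshold and excludes any drug effect, so it does not bound this trial.

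**Conclusion.** The concern holds. Followed as written, SAP 4.4 with 7.3 and 7.5 can omit a higher transaminase category, or a bilirubin rise first seen at a retest or early termination draw, from the summary meant to detect it.

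For retests after a required lab visit the exclusion is complete whenever the scheduled result exists. For early termination labs it applies in three 61-day ranges, assuming earlier visits were attended on target. Not all early termination data are lost: a result falling before the target day of a missed visit is used. The QTcF gap is smaller and turns on which window table applies.

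The effect is limited, because the triggering value is counted and a retest may be lower. The number of subjects affected cannot be derived from the documents. The change should be made because the omission is real and cheap to close; it does not affect the primary analysis.

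A separate, minor point is that protocol 1.16.1.11 has four severity levels and documents Grades 4–5 as life-threatening, while SAP 7.2 summarizes three levels with no stated mapping. The conclusion does not depend on it.

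**What to change.** - **SAP 7.3 and 7.5, add:** Threshold and outlier counts will also be presented by treatment arm at any time post-baseline, using each subject's worst post-baseline value from all scheduled, unscheduled, repeat and early termination assessments. Keep the by-visit tables as additional.
- **SAP 7.3, add:** Peak ALT or AST (× ULN) will be displayed against peak total bilirubin (× ULN) for each subject by treatment arm.
- **SAP 4.4:** state which assessments use Table 1 and which use Table 2, how results before the first window are handled, and that the any-time counts are exempt from the visit-selection rule.
- **SAP 7.2:** add a life-threatening row to both maximum-severity summaries, or state how Grades 4–5 are mapped.

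The cost is SAP wording, a few table shells and one figure. No new data are needed, since all laboratory and ECG results are already collected and listed.

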4.5. Analysis Sets

Analyses are to be performed on the following analysis sets as appropriate. The term ‘population’ is used interchangeably with ‘analysis set’.

- **Screened Set:** All subjects screened.
- **Intent to Treat (ITT) Set:** All randomized subjects. Subjects will be analyzed according to the randomized treatment group.
- **Full Analysis Set (FAS):** All randomized subjects who have received at least one dose of study drug irrespective of treatment received. In the event that FAS and ITT are identical, only FAS will be used. Subjects will be analyzed according to the randomized treatment group.
- **Per Protocol (PP) Set:** All randomized subjects who have completed the study with no major protocol deviations or problems. Major deviations or problems are those believed to have a material effect on the study outcome measures, including for example early dropouts, pharmacologically significant lapse in treatment, incorrect drug dispensed, test not performed according to manual of performance (MOP), machine or human technical error. The decision as to whether a subject is included in the PP set will be determined by Sponsor and made after blinded review of data and before any unblinded data analysis. Sponsor will generate a list of subjects excluded from PP, and such a list shall be incorporated in the final report.
- **Safety Set:** All subjects who have received at least one dose of study drug irrespective of treatment received. Subjects will be analyzed according to actual treatment received.
- **Pharmacokinetics (PK) Analysis Set:** All subjects who have received at least one dose of study drug and have at least one evaluable PK assessment. Subjects will be analyzed according to actual treatment received.

4.6. Handling of Incomplete/Missing, Unused, and Spurious Data

Missing data, incomplete data, or data not acquired according to the manual of performance, to the extent that it affects the accuracy or reliability of the measurement, will be removed from the presented analysis at the affected timepoints. Data that do not reflect a clinical or physiological phenomenon will be removed from the dataset during blind review.

